9.4.5 Immunogenicity Analyses

Antibodies against RO7296682 and atezolizumab will be evaluated in serum samples collected from all participants using appropriate assays. Listings and/or summaries will be prepared. Additional analyses may be conducted as appropriate.

The immunogenicity analyses will include all participants with at least one ADA assessment, irrespective of whether or not the participant receives any treatment ([Shankar et al. 2014](#)).

The numbers and proportions of ADA-positive participants and ADA-negative participants at baseline (baseline prevalence) and after study drug administration (post-baseline incidence during both the treatment and follow-up periods) will be summarized by dose levels and/or cohorts as appropriate.

- Participants are considered to be ADA positive if they are ADA negative or missing data at baseline and develop an ADA response following study drug administration (treatment-induced ADA response), or if they are ADA positive at baseline and the titer of one or more post-baseline samples is greater than the titer of the baseline sample by a scientifically reasonable margin such as at least 4-fold (treatment-enhanced ADA response). Treatment-induced ADA response can be further categorized in persistent (post-treatment ADA-positive samples over 16 weeks or more or the last ADA time point is positive) and transient (only one ADA-positive sample or the time between the first and last ADA-positive sample is less than 16 weeks and the last ADA sample is negative).
- Participants are considered to be ADA negative if they are ADA negative or missing data at baseline and all post-baseline samples are negative, or if they are ADA positive at baseline but do not have any post-baseline samples with a titer that is greater than the titer of the baseline sample by a scientifically reasonable margin such as at least 4-fold (treatment unaffected).

The relationship between ADA status and safety, efficacy, PK, and biomarker endpoints will be analyzed and reported descriptively via subgroup analyses.

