To characterize the pharmacodynamic (PD) effects of RO7296682 in combination with atezolizumab on peripheral blood cells and/or the tumor microenvironment.	
Correlate RO7296682 exposure and clinical endpoints with baseline levels and on-treatment changes of blood and tumor biomarkers, including but not limited to:
 
 • Treatment-induced changes in Treg levels in blood and/or tumor • Treatment-induced changes in Teff/Treg ratio of blood and tumor

Objectives	Endpoints
Exploratory (All Parts)	
To evaluate the anti-drug immune response after treatment with RO7296682 in combination with atezolizumab.	
 Incidence and titer of anti-drug antibodies (ADA) to RO7296682 during the study relative to the prevalence of ADA at baseline Incidence and titer of ADA to atezolizumab during the study relative to the prevalence of ADA at baseline
To evaluate the preliminary anti-tumor activity of RO7296682 when administered in combination with atezolizumab.	
 ORR DCR DoR PFS 
All according to iRECIST

To characterize PD effects and duration of PD response following the administration of RO7296682 in combination with atezolizumab.	
 Changes in number, frequency, activation status, and distribution of blood and tumor infiltrating lymphocytes (TILs) Immune contexture (i.e., expression levels of inhibitory or activation molecules on immune cells) Changes in circulating tumor DNA (ctDNA) levels (Parts II and III)
To explore biologic markers that might act as predictors of safety and/or anti-tumor activity of the combination of RO7296682 and atezolizumab.	
Including, but not limited to de novo occurrence and/or change from baseline in:
 
 Soluble molecules (e.g., levels and kinetics of inflammatory or inhibitory cytokines). Immune-phenotypic characteristics (i.e. levels of expression on immune cells of inhibitory or activation molecules). Tissue genetic factors (i.e., Teff, Treg, etc. gene signatures).
To explore the effect of Treg depletion in the skin immune contexture.	
 Treatment-induced changes in Treg levels in the skin as compared to baseline.
To explore degree of target binding of RO7296682 (in association with PK) via a receptor occupancy (RO) assay.	
 Evaluate RO via ex-vivo assay (Part I only)

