 - Participants with a history of autoimmune-mediated hypothyroidism who are on thyroid-replacement hormone are eligible for the study.
 - Participants with controlled type 1 diabetes mellitus who are on an insulin regimen are eligible for the study.
 - Participants with controlled eczema, psoriasis, lichen simplex chronicus, or vitiligo with dermatologic manifestations only (e.g., participants with psoriatic arthritis are excluded) are eligible for the study provided all of following conditions are met:
 - Rash must cover < 10% of body surface area.
 - Disease is well controlled at baseline and requires only low-potency topical corticosteroids.

- No occurrence of acute exacerbations of the underlying condition requiring psoralen plus ultraviolet A radiation, methotrexate, retinoids, biologic agents, oral calcineurin inhibitors, or high-potency or oral corticosteroids within the previous 12 months.

23. Prior treatment with CPIs, immunomodulatory agents and/or mAbs, and/or mAb-derived therapies, or immunostimulatory agents is not allowed (approved or investigational), provided that:

- Less than 4 weeks have elapsed between the last dose and the proposed C1D1.
- Less than 5 half-lives or 28 days (whichever is shorter) have elapsed since prior treatments with specific immunomodulators, TLR-agonists, inhibitors of IDO/TDO, or agonists (e.g., OX40) and the proposed C1D1.

24. For Part II only: Prior treatment with anti-CTLA4 is prohibited.

25. Prior treatment with a CC chemokine receptor 4 (CCR4)-targeting (e.g., mogamulizumab) or a CD25-targeting agent (e.g., basiliximab) is prohibited. Note: participants previously treated with single agent RO7296682 in the WP41188 study may be included in this study.

26. Treatment with standard radiotherapy, any chemotherapeutic agent, targeted therapy, or treatment with any other investigational drug (defined as treatment for which there is currently no regulatory authority-approved indication) within 28 days or 5 half-lives of the drug (whichever is shorter), prior to C1D1 is prohibited.

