6 CONGENITAL ANOMALIES/BIRTH DEFECTS

Any congenital anomaly/birth defect in a child born to a female participant or female partner of a male participant exposed to study treatment should be classified as a serious adverse event, recorded on the Adverse Event eCRF, and reported to the Sponsor immediately (i.e., no more than 24 hours after learning of the event).

Appendix 6

Study Details for Part III, NSCLC (Cohort A)

Background and Rationale for Part III, NSCLC Cohort

Lung cancer remains the leading cause of cancer death in the United States. Treatment of advanced-stage or metastatic non-small cell lung cancer (NSCLC) without EGFR mutations or ALK rearrangements has undergone significant advancement with the development of CPIs against PD-1/PD-L1 e.g., pembrolizumab, nivolumab, atezolizumab or durvalumab in the first line setting. Despite the recent advancements, patients respond poorly to CPIs and ultimately develop resistance mechanisms resulting in disease progression. Removing Tregs is postulated to increase the anti-tumor immunity of participants who do not respond to or progress following CPI treatment.

Should clinical benefit be observed in this or other trials fulfilling the gating criteria outlined in section 9.5, a NSCLC-specific cohort will be opened in order to investigate the signals further and in a wider population, without restrictions of [REDACTED] type or a specific prior CPI response pattern (i.e. as in Part II). As outlined in Section 4.2.1 of the protocol, given the high FoxP3 content (surrogate marker for Tregs) in this tumor type, Treg depletion through RO7296682 is postulated to increase anti-tumor activity in combination with anti-PD-L1 (atezolizumab).

Specific Inclusion Criteria for Part III, NSCLC Cohort

Participants are eligible to be included in the study only if all of the appropriate inclusion criteria listed in protocol Section 5.1 and all of the following criteria apply:

1. Participants with histologically confirmed advanced and/or metastatic NSCLC previously treated with CPI \pm platinum based chemotherapy, including PD-L1/PD-1/CTLA-4 inhibitors (investigational or approved) sequentially or concurrently with chemotherapy.
 - CPI administration as (neo-) adjuvant therapy is not allowed.
2. Participants whose tumors have known sensitizing mutations must also have experienced disease progression (during or after treatment) or intolerance to targeted therapy.

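### The ADA status used for the safety, efficacy, PK and biomarker subgroups is a treatment-emergence rule, so its negative reference group can include participants with pre-existing ADA

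*Combined protocol and SAP*

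**What the plan says.** Section 9.4.5 gives two routes into the ADA-negative class.

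- No antibody detected: "Participants are considered to be ADA negative if they are ADA negative or missing data at baseline and all post-baseline samples are negative".
- Antibody present before treatment and not boosted: "or if they are ADA positive at baseline but do not have any post-baseline samples with a titer that is greater than the titer" found at entry. How large a rise would count as boosting is given only by example, a 4-fold increase, and the plan itself tags this subset as treatment unaffected.

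Participants positive at baseline are also counted separately, because the summaries are to be given "at baseline (baseline prevalence) and after study drug administration (post-baseline incidence during both the treatment and follow-up periods"). Section 3 lists ADA as an exploratory objective with a matching endpoint: "Incidence and titer of anti-drug antibodies (ADA) to RO7296682 during the study relative to the prevalence of ADA at baseline".

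Section 9.4.5 closes with the use made of the classification: "The relationship between ADA status and safety, efficacy, PK, and biomarker endpoints will be analyzed and reported descriptively via subgroup analyses". It offers no other definition of ADA status for this step.

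**The concern.** Incidence and impact are different questions. For incidence, the right contrast is what treatment induced or boosted against what was already there, and the rule in 9.4.5 answers that. For impact, Section 8.6 gives the reason for measuring ADA: they might lower efficacy or cause hypersensitivity. Those consequences depend on antibody being present, whether or not treatment produced it.

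With a two-way label, a participant who enters with ADA and has no margin-sized titer rise joins the comparison group. If that participant reacts at the first infusion or has low troughs, the tables show this under ADA negative. The contrast between the classes could then be too small.

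The eligibility criteria leave room for such participants. The note to exclusion criterion 25 says that "participants previously treated with single agent RO7296682 in the WP41188 study may be included in this study". Inclusion criterion 22 requires prior anti-PD-1/L1 treatment in Part II, and Appendices 6 to 8 require prior checkpoint inhibitor treatment in Part III. Exclusion criterion 23 imposes a washout and does not bar prior atezolizumab.

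**Working it through.** The plan states no figure on this point, so there is nothing to reproduce. The check has two parts.

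**1. The text.** The unaffected class is wider than persistent carriers. It holds anyone positive at baseline whose later titers never exceed baseline by the margin. That includes participants who stay level, those who rise by less than the margin, and those who turn negative. Counting baseline prevalence separately shows how many there are, but does not take them out of the subgroup reference.

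**2. Possible size.** Every input below is an assumption except the group sizes: about 60 in Part II and about 20 per Part III cohort (Section 9.2).

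*Trough ratio.* Take N = 60 and 25% treatment-emergent ADA, so 60 × 0.75 = 45 are labelled negative. Let p be the share positive at baseline, with 80% of them unaffected. Unaffected carriers = 60 × p × 0.8, and s is their share of the 45. Suppose ADA halve troughs and unaffected pre-existing ADA act just as strongly. The observed ratio is 0.5 / (1 − 0.5 s). If they act half as strongly, it is 0.5 / (1 − 0.25 s).

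| p | Unaffected carriers | s | Ratio, equal effect | Ratio, half effect |
|---|---|---|---|---|
| 5% | 2.4 | 5.3% | 0.514 | 0.507 |
| 10% | 4.8 | 10.7% | 0.528 | 0.514 |
| 20% | 9.6 | 21.3% | 0.560 | 0.528 |

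The true ratio is 0.50 in every row.

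*Any difference between classes.* Let b be baseline prevalence, e the share of carriers boosted, i the treatment-induced incidence among the rest, and g the effect of unboosted pre-existing ADA relative to treatment-emergent ADA. The carrier share of the negative class is f = b(1 − e) / [b(1 − e) + (1 − b)(1 − i)], and the retained contrast is 1 − g f. Example: b = 0.10, e = 0, i = 0.20 gives f = 0.10 / (0.10 + 0.90 × 0.80) = 0.122, so 0.878 is retained at g = 1. With e = 0 and i from 5% to 40%:

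| b | f | Retained, g = 1 | Retained, g = 0.5 |
|---|---|---|---|
| 1% | 0.011 to 0.017 | 0.989 to 0.983 | 0.995 to 0.992 |
| 5% | 0.052 to 0.081 | 0.948 to 0.919 | 0.974 to 0.960 |
| 10% | 0.105 to 0.156 | 0.895 to 0.844 | 0.948 to 0.922 |
| 20% | 0.208 to 0.294 | 0.792 to 0.706 | 0.896 to 0.853 |

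At b = 0 or g = 0 nothing is lost.

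*Expected baseline carriers.* In a cohort of 20: 0.2 at 1% prevalence, 1 at 5% and 2 at 10%, with chances of none of 82%, 36% and 12%. In 60 participants: 0.6, 3 and 6.

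**The case against.** A reader might infer that the reference group does contain carriers and that the ADA effect is diluted. The documents support neither. Both need a non-zero baseline prevalence and an effect of stable, pre-existing antibody on outcome, and neither is given.

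The evidence on carriers is thin. For RO7296682, Section 2.2 reports that preliminary single-agent data showed no treatment-emergent ADA in treated patients, which points against the WP41188 route. For atezolizumab, Appendix 6 mentions "pembrolizumab, nivolumab, atezolizumab or durvalumab in the first line setting", but that is background on lung cancer care and does not describe the participants. How many had atezolizumab before is not stated. Exclusion criteria 2 to 4 also remove people with known hypersensitivity to either drug, severe anaphylactic reactions to chimeric or humanized antibodies, or Grade 3 or higher infusion reactions on an earlier checkpoint inhibitor, so some of the most relevant carriers are screened out.

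The section also names the induced, enhanced and unaffected categories, provides for listings, and leaves room for further analyses. Individual data to identify carriers are collected. ADA is exploratory, Section 9.1 plans no formal testing, and no futility rule or cohort-opening criterion uses ADA status.

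All of this stands as a limit on size and importance. It does not settle which ADA status the subgroup sentence means: optional further analyses specify nothing, and the only available definition places carriers with the negatives.

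**Conclusion.** The point holds in conditional form. As written, the negative reference group for the ADA-impact subgroups can include participants with pre-existing ADA, and any ADA effect may then be understated. The incidence rule itself is coherent; it would be wrong to read this point as a fault in it.

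The size is unknown. The shift from 0.50 to between 0.51 and 0.56 rests on assumed prevalence, boosting, incidence and effect, and on pre-existing ADA acting as strongly as treatment-emergent ADA. At half that strength the shift is to between 0.507 and 0.528, and it can be zero. No primary or secondary endpoint, sample size or decision rule is touched. This is a low-priority improvement to an exploratory, descriptive analysis.

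**What to change.** Keep the present treatment-induced and treatment-enhanced rule for incidence. Add a sentence to 9.4.5 saying that the ADA-impact subgroups will be shown separately for each drug in three groups:

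1. no ADA at any time, as the reference;
2. ADA positive at baseline and treatment-unaffected;
3. treatment-induced or treatment-enhanced ADA.

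Where group 2 is too small to summarise, give it as a listing.

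The cost is that sentence and one more column in the tables. No new samples are needed: Tables 2 and 3 already schedule pre-dose ADA for both drugs on Day 1 of Cycle 1 and at later visits. The downside is a small middle group (2.4 to 9.6 of 60 under the assumptions above, and possibly nobody in a cohort of 20), which will rarely support a conclusion of its own. Its main value is to keep known carriers out of the reference.

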Safety FU (135d after last dose)		At visit		x	x	x	x												x	x	
In addition, samples to be taken at the following instances:																					
In the event of an IRR/CRS ≥ G2 or with clinical signs of hypersensitivity reaction		At visit		x	x	x	x												x		
DLT		At visit		x	x	x	x				x	x							x		
Unscheduled Visit		At visit		x	x	x	x	x	x	x	x	x						x			
Any visit																					

Footnotes for Table 2 and Table 3

a	All blood samples for PK assessments will be collected from an IV line in the opposite arm to the one for drug infusion. All times after EOI timepoint are to be taken from the end of infusion. Post dose samples except EOI are to be taken from the time of RO7296682 administration.
b	
Up to Cycle 5: PK and ADA samples should be taken at indicated timepoints.
 
Subsequent cycles until 6 months after 1st dose: PK and ADA samples will be taken on Day 1 of each cycle.
 
Subsequent cycles after first 6 months of treatment: PK and ADA samples will be taken only Day 1 at cycle of tumor assessments.

c	PK samples will be taken (where feasible) at the time of development of any of the following events, or at the earliest possible convenience thereafter: 
 * DLT * Dose reduction or treatment reduction or interruption due to IRR event \geq Grade 2 or hypersensitivity 
 - At time of interruption, collect the unscheduled PK sample and clearly record the reason this collection (i.e., due to interruption) - At infusion restart and completion, collect scheduled pre, (mid – where applicable) and post infusion time-points as noted per SoA . Note: the re-start time after the dose interruption is taken as the reference timepoint.
d	Tryptase and IgE samples will be collected for local analysis at onset of the reaction. If tryptase and/or IgE are elevated, a second sample for central IgE/tryptase analysis will be collected approximately 48 hours after onset of the reaction.
e	
Mandatory fresh tumor biopsies collected at baseline and C2D8 for:
 
 - Part II and Part III participants only 
Mandatory healthy skin punch biopsies collected at baseline and C2D8 for:
 
 - All Parts (I, II and III)

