8.6 IMMUNOGENICITY ASSESSMENTS

Although RO7296682 and atezolizumab are humanized antibodies, there is a risk that ADAs against RO7296682 or atezolizumab could develop. This could potentially reduce their efficacy and/or potentially result in symptomatic hypersensitivity reactions, in particular immune-complex reactions, or both.

Validated screening, confirmatory, and titer assays will be employed to detect potential ADAs against RO7296682 and atezolizumab at multiple time points before, during, and after treatment. If required, ADA-positive samples will be further characterized in exploratory assays.

Blood samples for ADA determination will be obtained as specified in the SoA (Section 1.3). The date and time of each sample will be recorded in the eCRF.

Additional ADA samples will be drawn at the time of treatment discontinuation or at the safety follow-up visits and in participants who experience a Grade ≥ 2 IRR and in participants with clinical signs of hypersensitivity reaction, in particular immune-complex reactions. In any case, for each collected ADA sample, a corresponding PK sample will be collected at the same time point for the determination of the RO7296682 and/or atezolizumab concentrations. See Section 1.3 for details.

Remaining volumes of ADA samples may be used for assay development/validation experiments, for compound-related exploratory analyses (e.g. PK or biomarker profiling), or to help develop further blood tests, after they are used for the mentioned intended uses.

The ADA blood samples will be destroyed within 2 years after the date of the final CSR.

Details on sampling procedures, sample storage and shipment are documented in the sample documentation.

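### Grouping participants by ADA status acquired during the study biases PFS, OS and response in favour of ADA positives and adverse events against them, by an amount the documents cannot fix

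*Combined protocol and SAP*

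**What the plan says.** **Classification.** Under Section 9.4.5 one qualifying post-baseline sample, treatment-induced or treatment-enhanced, makes a participant ADA positive. The main route to being negative is "ADA negative or missing data at baseline and all post-baseline samples are negative". The window is open-ended: "post-baseline incidence during both the treatment and follow-up periods". The planned use is: "The relationship between ADA status and safety, efficacy, PK, and biomarker endpoints will be analyzed and reported descriptively via subgroup analyses".

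**Sampling.** Tables 2 and 3 in Section 1.3 schedule ADA at predose on Day 1 of Cycles 1 to 5. Footnote b then says, up to 6 months after first dose, "PK and ADA samples will be taken on Day 1 of each cycle", and after that "PK and ADA samples will be taken only Day 1 at cycle of tumor assessments". The tables also list the end-of-treatment visit (28 days after last dose) and the safety follow-up (135 days). Section 8.6 adds: "Additional ADA samples will be drawn at the time of treatment discontinuation or at the safety follow-up visits", plus samples after a Grade ≥ 2 IRR or signs of hypersensitivity.

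**Outcomes.** Section 9.4.2 starts PFS at C1D1 and OS at first dose. Section 7.2 has treatment ending at progression, unacceptable toxicity or withdrawal of consent. Section 9.4.3 summarises safety descriptively with no exposure adjustment. No landmark or time-dependent ADA status appears in Sections 9.4.2, 9.4.3 or 9.4.5.

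**The concern.** The groups are formed with information that did not exist at time zero. To be found positive at a late cycle, a participant must have stayed on treatment until that cycle, which usually means not having progressed. That event-free time is credited to the positive group from C1D1. Participants who progress early leave the sampling schedule early and tend to fall in the negative group.

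Section 8.6 gives two reasons for measuring ADA: possible loss of efficacy and hypersensitivity. The planned comparison distorts both, in opposite directions. On efficacy, ADA positives look better than they are. On safety, they have had longer exposure in which to have an event, and reactions themselves trigger more ADA testing, so they look worse.

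**Working it through.** **Inputs from the documents:** a cycle of 21 days; the ADA schedule above; scans every 8 weeks (± 7 days) in year one (Section 8.1.1); PFS from C1D1. The plan states no ADA rate, onset time or effect for the combination, so it has no figure of its own to reproduce. Everything below on ADA onset, PFS, survival after progression and AE hazard is an assumption.

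**Step 1, by hand.** Assume 5% conversion per 3 weeks, unrelated to outcome and continuing after the last dose. The chance of being found positive by a last sample on day t is 1 − 0.95^(t/21).

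- Progression at the week 8 scan (day 56): last dose C3D1, day 42. On-treatment samples only: 1 − 0.95² = 9.75%. With the sample 135 days later (day 177): 1 − 0.95^8.43 = 35.1%.
- Progression at week 26 (day 182): last dose day 168. On-treatment samples only: 1 − 0.95⁸ = 33.7%. With the 135-day sample (day 303): 1 − 0.95^14.43 = 52.3%.

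The later progressor is 33.7/9.75 = 3.5 times as likely to be classed positive on treatment samples alone, and 52.3/35.1 = 1.5 times as likely once the 135-day sample is obtained. If all onset is by week 6, both participants have a sample on or after day 42 and the imbalance disappears.

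**Step 2, simulation with no ADA effect.** 400,000 participants in each of 24 scenarios: exponential PFS with median 2, 3 or 5 months; ADA incidence 10% or 30%, either at constant hazard (that share by week 26) or all within weeks 1 to 6; median survival after progression 6 months; sampling every 3 weeks, with or without the 28-day and 135-day samples. The apparent hazard ratio is the ratio of events per person-time from C1D1, ever-positive over never-positive. Crude AE shares use 1 − exp(−0.15 × (months of exposure + 1)).

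| ADA onset | Post-treatment samples | Apparent PFS HR | Crude AE share, positive v negative (median PFS 3 months, ADA 30%) |
|---|---|---|---|
| Gradual | No | 0.41–0.49 | 66% v 40% |
| Gradual | Yes | 0.50–0.65 | 55% v 40% |
| Weeks 1–6 | No | 0.66–0.85 | 53% v 43% |
| Weeks 1–6 | Yes | 0.94–0.98 | 46% v 45% |

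The true hazard ratio is 1 throughout. Time-dependent ADA status gives 0.98–1.01 and a week 6 landmark 0.99–1.01 in all 24 scenarios. The AE column leaves out event-triggered sampling, which would widen the gap.

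**Step 3, closer to the schedule.** Median PFS 2.5 months, 5% conversion per 3 weeks, response possible only if PFS exceeds 16 weeks and then with probability 0.5.

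| ADA samples and scans | Median PFS (months), positive v negative | HR | ORR |
|---|---|---|---|
| Each cycle plus end of treatment | 5.1 v 2.0 | 0.46 | 32% v 14% |
| Adding the 135-day sample | 3.9 v 2.0 | 0.56 | not listed |
| Also detecting progression on the 8-week grid | 3.7 v 3.7 | 0.67 | 25% v about 14% |

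A C4D1 (week 9) landmark restores a hazard ratio of about 1.0, with ORR 32% v 32% in the first of these settings.

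**Step 4, cost of a landmark.** At median PFS 2.5 months (30.4 days per month), the share progressed by day 56 is 1 − 2^(−56/76) = 40%, and by day 63 it is 1 − 2^(−63/76) = 44%. In a 20-participant Part III cohort, about 0.56 × 20 = 11 remain at C4D1, of whom 1 − 0.95³ = 14% are positive: one or two people.

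**The case against.** **It is descriptive and exploratory.** Section 9.1 plans no hypothesis test, ADA is an exploratory endpoint in Table 4, and ADA status enters neither the criteria for opening Part III cohorts nor the futility rules. This stands and limits the importance. It does not remove the bias: the subgroup medians and rates would still be reported, and more participants would not correct them.

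**Follow-up samples close the gap.** They do in part. A reader might infer that early progressors are negative because they were sampled only once or twice. The schedule does not support that: someone progressing at the first scan has C2D1, C3D1, end-of-treatment and 135-day samples, four if alive and attending. Treatment beyond progression (Section 7.1) adds more. Only those who die or leave sooner have few.

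**No ADA has been seen.** Section 2.2 reports no treatment-emergent ADA so far, but those are preliminary single-agent data for RO7296682. They do not cover the combination or atezolizumab ADA.

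**The same flaw affects biomarkers.** Table 4 plans to "Correlate RO7296682 exposure and clinical endpoints with baseline levels and on-treatment changes of blood and tumor biomarkers", and a reader might extend the argument to all of these. For the C2D8 biopsies (about day 29) it is minor, because they precede the first scan. It matters only for later on-treatment samples.

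**A landmark yields little in small cohorts.** This stands, as step 4 shows, and is a reason to allow the time-dependent form.

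**Conclusion.** The bias follows from the definitions in Section 9.4.5 read with the time origins in 9.4.2, and the remedy is inexpensive, so the change is worth making. It is a limitation of an exploratory, descriptive comparison and does not touch the primary endpoints.

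The direction differs by outcome. PFS, OS and response favour ADA positives; crude AE frequencies go against them. A reader might infer that ADA would look harmless throughout. For safety the documents point the other way, given longer exposure and the reaction-triggered samples in Section 8.6.

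The size is not established. With no true effect the apparent PFS hazard ratio runs from about 0.4 (gradual onset, no safety follow-up sample), through about 0.5–0.67 (gradual onset with the 135-day sample, with or without the 8-week scan grid), to 0.94–0.98 (onset in weeks 1–6 with follow-up samples). Taking the 0.4 end as the expected distortion would ignore scheduled samples and assume an onset pattern the documents do not give. The OS bias was not quantified.

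**What to change.** In Section 9.4.5:

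1. Keep ever-positive status for reporting ADA incidence only.
2. Relate ADA to PFS, OS and response by status at a fixed early visit, for example C3D1 or C4D1 predose, among participants still at risk, counting outcomes after that visit. Alternatively, for PFS and OS, use a time-dependent ADA status. C3D1 (day 42) falls before the earliest first scan (day 56 − 7 = 49). C4D1 (day 63) does not, so choosing it requires a rule for first-scan responses.
3. Report AEs by ADA status as exposure-adjusted rates, or as events after the first positive sample, and show ADA results from event-triggered samples separately.
4. Apply the same landmark principle to on-treatment biomarkers sampled later than C2D8.

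This is wording only and needs no new samples. The price of a landmark is that late seroconverters count as negative, and participants who progress or leave beforehand drop out of the comparison: about 40–44% by week 9 if median PFS is 2.5 months. The time-dependent version may therefore be preferable in the small cohorts.
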